5.5.2 Replacement of Patients

Patients who are enrolled but do not proceed to conditioning with a Treosulfan-containing regimen will be described (frequency, reason for not proceeding to conditioning), but they will not count towards the target accrual of n=40 patients conditioned with a Treosulfan-containing regimen.

5.5.3 General Analysis Guidelines

Primary analyses for the primary, secondary, safety, and exploratory endpoints will use the primary analysis population. Analyses of each endpoint will follow the analysis plans as described below in **sections 5.6-5.8**. We expect minimal missing data (<5%) for the primary endpoint and secondary endpoints based on past experience with HCT and cellular therapy trials. If more than 10% of a key primary or secondary outcome is missing, we will apply an appropriate imputation method and conduct corresponding sensitivity analyses.

5.6 Analysis of Primary Endpoint

The probability of GEFS at 1 year will be estimated using the Kaplan-Meier method, along with 95% confidence intervals computed using a complementary log-log transformation.

5.7 Analysis of Secondary Endpoints

Analysis of secondary endpoints will be primarily descriptive, using estimates along with 95% confidence intervals as detailed below.

5.7.1 Overall Survival

The probability of OS at 1 year will be estimated using the Kaplan-Meier method, along with 95% confidence intervals computed using a complementary log-log transformation.

5.7.2 GVHD-Free, Event-Free Survival

GVHD-free, event-free survival will be estimated at 1 year using the Kaplan-Meier method, along with 95% confidence intervals computed using a complementary log-log transformation.

5.7.3 Hematologic Recovery

Probabilities of neutrophil recovery by Day 28 and Day 100 will be described with 95% confidence intervals using the cumulative incidence estimate, treating death as a competing event. Complementary log-log transformations will be used to construct the confidence intervals. Similarly, probabilities of platelet recovery by Day 100 will be described with 95% confidence intervals using the cumulative incidence estimate, treating death as a competing event.

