2.5.5.6 Management of Graft Failure

Graft failure will be managed as per institutional guidelines.

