3.2.3 Hematologic Recovery

Hematologic recovery will be assessed according to neutrophil and platelet counts recovery after transplant. Neutrophil recovery will be estimated at day 28 and platelet recovery at day 100 after HCT.

Neutrophil recovery is defined as achieving an absolute neutrophil count (ANC) $\geq 500/\text{mm}^3$ for 3 consecutive measurements on 3 different days. The first of the three days will be designated the day of neutrophil recovery. The competing event is death without neutrophil recovery.

Platelet recovery is defined as the first day of a minimum of 3 days that the patient has a sustained platelet count $\geq 20,000/\text{mm}^3$ with no platelet transfusions in the preceding 7 days. The first day of sustained platelet count above these thresholds will be designated the day of platelet engraftment.

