3.2.4 Donor Chimerism (CD3 and Myeloid)

Donor cell engraftment will be assessed with donor/recipient chimerism studies at day 28, 100, 180, and 1 year after HCT. Chimerism will be evaluated in fractionated blood for CD3 T-cell and myeloid (CD33 or CD15). Peripheral blood myeloid donor chimerism will be used to define the donor/recipient chimerism status.

Full donor chimerism is defined as $\geq 95\%$ donor cells in the myeloid fraction.

Mixed donor chimerism/engraftment is defined as the presence of 5-94.99% donor cells in the myeloid fraction.

Graft rejection is defined as $< 5\%$ donor cells in the myeloid fraction.

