5.7.4 Donor Chimerism (CD3 and Myeloid)

Proportions of patients with full (>95%), mixed (5-95%), or rejection (<5%) myeloid chimerism will be tabulated and described using frequencies and percent at each time point.

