5.7.5 Acute GVHD

Cumulative incidence of acute grade II-IV GVHD will be estimated using the cumulative incidence function, treating death prior to acute GVHD as a competing risk. Point estimates and confidence intervals will be provided for the cumulative incidence at day 100 and day 180 post-HCT, using the complementary log-log transformation. Time to GVHD will be calculated from transplant date. Cumulative incidence of acute grade III-IV GVHD will be estimated using the cumulative incidence function, treating death prior to acute GVHD as a competing risk. Point estimates and confidence intervals will be provided for the cumulative incidence at day 100 and day 180 post-HCT.

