5.7.6 Chronic GVHD

Cumulative incidence of chronic GVHD requiring immune suppression (IS) will be estimated using the cumulative incidence function, treating death prior to chronic GVHD as a competing risk. A point estimate and confidence interval will be provided for the cumulative incidence at 6 months and one-year post-HCT, using the complementary log-log transformation. Frequencies of NIH global severity scores of mild, moderate, and severe will also be provided.

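### Recovery on a rescue graft counts as neutrophil or platelet recovery by Day 100, because death is the only competing event named

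*Protocol*

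**What the plan says.** Section 3.2.3 of the protocol defines neutrophil recovery by absolute neutrophil count (ANC) alone and adds: "The competing event is death without neutrophil recovery". Section 5.7.3 repeats the choice for the analysis: the neutrophil endpoint "by Day 28 and Day 100 will be described with 95% confidence intervals using the cumulative incidence estimate, treating death as a competing event". It then continues: "Similarly, probabilities of platelet recovery by Day 100 will be described with 95% confidence intervals using the cumulative incidence estimate", again with death as the competing event.

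For chimerism, section 3.2.4 states: "Peripheral blood myeloid donor chimerism will be used to define the donor/recipient chimerism status". Section 5.7.4 says the categories "will be tabulated and described using frequencies and percent at each time point". Neither section says what happens to a patient who has had a second graft.

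The GVHD analyses follow the same pattern. Section 5.7.5 uses the cumulative incidence "treating death prior to acute GVHD as a competing risk" and section 5.7.6 "treating death prior to chronic GVHD as a competing risk".

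Elsewhere the protocol treats a second transplant as failure of the first. It is an event in GEFS (3.1.1) and EFS (3.2.2). Section 3.2.2 also counts a second infusion of cells as a sign of primary graft failure up to day +42 and of secondary graft failure. Rescue itself is left to the sites: "Graft failure will be managed as per institutional guidelines". Section 5.5.1 keeps every patient conditioned with Treosulfan in the analysis.

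**The concern.** The recovery endpoints are meant to show how well the study transplant engrafts. Under the stated rule, a patient with no ANC recovery stays at risk after a second transplant and is counted as a success if the rescue graft takes before day 100. The same patient is a primary graft failure under section 3.2.2. The Day 100 estimates then mix engraftment of the study graft with engraftment of a later one, and the error favours the regimen.

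Chimerism has a related gap. Status rests on donor percentage alone, so a rescued patient can leave the rejection category at later time points. Because that analysis is a cross-sectional table, the defect there is a missing rule for patients after rescue, not a wrong competing event.

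**Working it through.** **1. Can one patient be both a failure and a recovery?** Take a patient with no ANC recovery who receives a second infusion by day +42 and first reaches an ANC of 500 on three different days between then and day 100.
- Section 3.2.2: primary graft failure, hence an EFS event and a GEFS event.
- Sections 3.2.3 and 5.7.3: no death, ANC criterion met before day 100, hence recovered by Day 100.

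No other section censors, excludes or reclassifies the patient, so both classifications apply.

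**2. Who moves the estimate?** A patient does so only if all three hold: the recovery definition had not been met before the second transplant; a second transplant took place; recovery followed by day 100. Two groups of graft failures drop out for neutrophils:
- Secondary failures: section 3.2.2 requires documented haematopoietic recovery beforehand.
- Failures on chimerism alone: section 3.2.3 has no donor-cell requirement, so host recovery already meets the ANC definition without any rescue.

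**3. Size per patient.** With no censoring before day 100, the cumulative incidence is a simple proportion, so each affected patient adds 1/40 = 2.5 points.

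**4. Upper bound on the expected shift.** Inputs: n = 40 (section 5.5.2); day-100 graft failure g = 3.8% with ATG in the registry data (section 1.3.2) or 10%, the highest rate expected (section 5.3). Let q be the share of graft failures meeting all three conditions in step 2. The protocol gives no value for q, so it is an assumption. Affected patients = 40 × g × q; shift in points = 100 × g × q.

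| g | Expected failures | q = 0.5 | q = 1 (ceiling) |
|---|---|---|---|
| 3.8% | 40 × 0.038 = 1.52 | 0.76 patients, 1.9 points | 1.52 patients, 3.8 points |
| 10% | 40 × 0.10 = 4.0 | 2 patients, 5 points | 4 patients, 10 points |

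At q = 0 the shift is zero. The chance of at least one graft failure among 40 is 1 − 0.962^40 = 79% at 3.8% and 1 − 0.90^40 = 98.5% at 10%.

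**5. What it does to a reported interval.** The exact limits in Table 15 reproduce: 38/40 gives 83.1 to 99.4% (stated 83-99%) and 36/40 gives 76.3 to 97.2% (stated 76-97%). Suppose four patients have no recovery on the study graft, nobody dies, and two of the four recover on a rescue graft by day 100. Day 100 recovery then reads 38/40 = 95% as written, against 36/40 = 90% with second HCT as a competing event. With a log(−log) transformation of the cumulative incidence the intervals are 81.5 to 98.7% and 75.5 to 96.1%.

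**6. Time points.** Primary failure is assessed by day +42, so few rescue grafts could produce recovery by day 28. The exposed figures are Day 100 neutrophil and platelet recovery and the later chimerism tables.

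**The case against.** The strongest reply is that these are descriptive secondary endpoints with no test attached, and that data after a second transplant are often handled in the statistical analysis plan, which is not at hand. The first half stands and limits the importance of the point. The second half is weaker: the protocol is not silent but names the competing event, in both the endpoint definition and the analysis section for neutrophils.

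A reader might also infer more than the protocol supports:
- *That graft failure is hidden.* It is not. It counts in GEFS and EFS, is a secondary objective of its own, and is monitored against a boundary in section 5.3.
- *That the recovery result contradicts GEFS or EFS.* Failure of the study graft and later blood-count recovery can both be true of one patient. The problem is attribution.
- *That Day 100 recovery would read 100% instead of 90%.* That needs all four failures at the 10% rate to lack prior recovery, to be re-transplanted and to recover in time. Step 2 shows why this is an extreme.
- *That a rescued patient is certain to be tabulated as full donor.* Chimerism uses patient and donor samples taken before enrolment (section 4.3.3). If the second donor differs, the protocol does not say whether those cells would be scored as donor.
- *That counting GVHD after rescue flatters the regimen.* It works the other way, raising the GVHD incidence. Counting all GVHD after the study transplant is a defensible choice.

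**Conclusion.** The point holds for neutrophil and platelet recovery at Day 100: as written, recovery on a rescue graft is credited to the study transplant. The size is 2.5 points per affected patient. In expectation it is at most about 1.5 patients at 3.8% graft failure and 4 patients (10 points) at 10%, and probably less. These ceilings assume that every failure is rescued, had not already recovered, and recovers by day 100; the protocol gives no rescue rate or timing. For chimerism the defect is a missing rule for re-transplanted patients. For GVHD a change is optional. Day 28 recovery is little affected. GEFS, EFS and the graft-failure monitoring rule are not affected, because the failure itself is counted there, and OS follows patients regardless of a second transplant.

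**What to change.** - **Sections 3.2.3 and 5.7.3:** for neutrophil and platelet recovery, replace death as the competing event with death or second HCT/second infusion, whichever is first, taking second infusion as in section 3.2.2.
- **Section 5.7.4:** after a second HCT, show the patient in a separate rejection / second HCT row at each later time point instead of classifying by donor percentage alone.
- **Sections 5.7.5 and 5.7.6 (optional):** treat second HCT as a competing risk for GVHD, in the main analysis or as a sensitivity analysis.

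The cost is wording in a few paragraphs. The date of a second transplant is already needed for GEFS, so no new data are collected, and clinical management does not change. The downside is that Day 100 recovery figures may be slightly less favourable.

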5.7.4 Donor Chimerism (CD3 and Myeloid)

Proportions of patients with full (>95%), mixed (5-95%), or rejection (<5%) myeloid chimerism will be tabulated and described using frequencies and percent at each time point.

5.7.5 Acute GVHD

Cumulative incidence of acute grade II-IV GVHD will be estimated using the cumulative incidence function, treating death prior to acute GVHD as a competing risk. Point estimates and confidence intervals will be provided for the cumulative incidence at day 100 and day 180 post-HCT, using the complementary log-log transformation. Time to GVHD will be calculated from transplant date. Cumulative incidence of acute grade III-IV GVHD will be estimated using the cumulative incidence function, treating death prior to acute GVHD as a competing risk. Point estimates and confidence intervals will be provided for the cumulative incidence at day 100 and day 180 post-HCT.

5.7.6 Chronic GVHD

Cumulative incidence of chronic GVHD requiring immune suppression (IS) will be estimated using the cumulative incidence function, treating death prior to chronic GVHD as a competing risk. A point estimate and confidence interval will be provided for the cumulative incidence at 6 months and one-year post-HCT, using the complementary log-log transformation. Frequencies of NIH global severity scores of mild, moderate, and severe will also be provided.

5.7.7 Grade 3-5 Toxicities

All grade 3-5 toxicities according to CTCAE version 5.0 will be categorized by SOC and preferred term using the MedDRA dictionary, and the number of AEs will be summarized by SOC, preferred term, and peak grade. The number and percentage of patients with at least 1 grade 3 or higher AE will be summarized by SOC and the preferred term. Detailed listings of unexpected SAEs, including severity and relationship to treatment, will be presented.

5.7.8 Systemic Infections

The number of microbiologically documented infections or significant infections requiring antibiotic/antifungal/antiviral therapy and the number of patients experiencing infections will be tabulated by type of infection, severity, and time period after transplant. The cumulative incidence of CMV reactivation or EBV reactivation requiring therapy will be estimated at 180 days with a 95% confidence interval, treating death as a competing risk.

5.8 Analysis of Exploratory Endpoints

5.8.1 PK Studies, Biological Studies, and Mutational Testing

Analyses of lab sample endpoints will be described in a future statistical analysis plan separate from this protocol. This protocol only describes processes for collection of the samples.

5.8.2 Health-Related Quality of Life

PROMIS Scale total score and subdomain scores will be summarized using means and SDs at baseline, 6 months, and 1 year. Changes from baseline to day +180 and day +365 post-HCT will be analyzed using the paired t-test and linear mixed models for longitudinal data.

APPENDIX A
HUMAN SUBJECTS PROTECTION

APPENDIX A HUMAN SUBJECTS

1. Subject Consent

Candidates for the study will be identified as described in **Chapter 4** of the protocol. The Principal Investigator or his/her designee at each transplant center will contact the candidates, provide them with information about the purpose of the study and obtain voluntary consent if the candidates agree to participate. The BMT CTN will provide a template of the assent and the consent forms to each center. Each center will add their NMDP IRB-approved boiler-plate language to these documents and submit it for review by the NMDP Internal Review Board (IRB). The DCC will verify the adequacy of the assent and consent forms prior to submission to the IRB. The NMDP IRB will provide evidence of IRB approval.

2. Confidentiality

Confidentiality will be maintained by individual names being masked and assigned a patient identifier code. The code relating the patient's identity with the ID code will be kept separately at the center. The ID code will be transmitted to the network.

Participation of Women and Minorities

Women and ethnic minorities and other populations will be included in this study. Accrual of women and minorities at each center will be monitored to determine whether their rates of enrollment are reflective of the distribution of potentially eligible women and minorities expected from data reported to the CIBMTR and from published data on incidence of leukemia and lymphoma in these groups. Centers will be notified if their rates differ significantly from those expected and asked to develop appropriate recruitment reports.

[figure not shown]
3. GCP

This study will be conducted in accordance with standards of Good Clinical Practice (as defined by the International Council for Harmonization) and all applicable national and local regulations.

APPENDIX B
PROTOCOL ELIGIBILITY REVIEW COMMITTEE

APPENDIX B

ELIGIBILITY REVIEW COMMITTEE

Patients with the following BMFD are eligible for this protocol:

1. Shwachman-Diamond syndrome
2. Diamond Blackfan Anemia
3. Congenital Sideroblastic anemia
4. *GATA2* mutation with associated marrow failure
5. *SAMD9* or *SAMD9L* disorders
6. Congenital amegakaryocytic thrombocytopenia
7. Paroxysmal nocturnal hemoglobinuria
8. An undefined BMFD: a patient with a BMFD for whom a genetic mutation responsible for their bone marrow failure phenotype has not been identified (excluding PNH) will be eligible for this clinical trial following approval by BMT CTN 1904 ERC.
9. A BMFD with a known genetic mutation but not listed above will be eligible for this clinical trial following approval by BMT CTN 1904 ERC.

The following patients MUST be reviewed by the BMT CTN 1904 protocol eligibility review committee (ERC) in order to determine if they are eligible for this trial:

1. All patients with Shwachman-Diamond syndrome, Diamond Blackfan anemia, congenital sideroblastic anemia, or congenital amegakaryocytic thrombocytopenia who have had genetic testing and a genetic mutation responsible for their disease was not identified.
2. All patients with an undefined BMFD: a patient with a BMFD for whom a genetic mutation responsible for their bone marrow failure phenotype has not been identified, excluding PNH.
3. All patients with a BMFD and a known genetic mutation that is not listed above
4. All patients with *GATA2* mutation with associated marrow failure
5. All patients with *SAMD9* or *SAMD9L* disorders
6. There may be circumstances where a treating physician will consider a transplant for a patient with a BMFD who does not meet all the criteria listed under “indications for HCT”. In these situations, treating physicians may submit their patient to the BMT CTN1904 ERC for review in order to determine if the patient is eligible for this clinical trial based on additional clinical or laboratory information.
7. Many patients with BMFD can have bone marrow evaluations that raise concern for possible MDS including but not limited to dysplastic bone marrow evaluations or cytogenetic abnormalities. However, in patients with BMFD these findings are not necessarily diagnostic or consistent with MDS. Therefore, given the complexities of diagnosing MDS in patients with BMFD, all patients with bone marrow evaluations concerning for possible MDS should be submitted to the ERC for review to confirm or exclude MDS. This is particularly important as we do not want to exclude potentially eligible patients due to an incorrect diagnosis of MDS.

The protocol ERC will consist of a minimum of 3 members of the BMT CTN protocol 1904 team. All potential patients will be identified by their local transplant physician who will determine if the patient meets the eligibility criteria for BMT CTN 1904.

Once the patient has signed the consent for this study, certain screening information outlined below will need to be submitted to the protocol ERC who will review and confirm whether the patient is eligible for BMT CTN 1904 protocol. As outlined above, there are specific situations that require

ERC review. For example, patients who lack a genetic mutation following genetic testing. In addition, we also recognize there **may be circumstances where the transplant physician will consider a transplant for a patient with a BMFD who does not meet all the criteria listed under “indications for HCT”**. **In these situations, the transplant physician may submit their patient to the BMT CTN 1904 ERC for review in order to determine if the patient is eligible for this clinical trial based on additional clinical or laboratory information.**

The patient does NOT have to complete the pre-transplant evaluations specified in BMT CTN 1904 prior to ERC review. However, the ERC may ask for additional patient data to determine protocol eligibility which may include some of the clinical assessments recommended/required by the protocol. If the ERC deems the patient eligible for BMT CTN 1904, the patient will need to complete the recommended/required baseline pre-transplant clinical assessments in the time period outlined in the protocol. The patient must also continue to meet protocol eligibility criteria as outlined in BMT CTN 1904 at time of study enrollment and at the time of starting conditioning.

The following screening information is recommended and should be uploaded in Advantage eClinical prior to ERC review:

1. Disease Assessments:

- a. All genetic testing available including genetic testing that was negative for a mutation (this excludes patients with PNH)
- b. Patients who lack a genetic mutation (excluding patients with PNH) must have negative testing for Fanconi anemia via Diepoxybutane (DEB) or Mitomycin C (MMC) testing on peripheral blood or skin fibroblasts (at any time prior to screening assessment for disease eligibility). Centers should upload testing results even if normal.
- c. Patients who lack a genetic mutation (excluding patient with PNH) must have telomere testing by flow-FISH. Centers should upload testing results even if normal.
- d. For patients with PNH: flow cytometry for PNH per institutional practice.
- e. Additional disease specific evaluations should also be included (if performed) if a genetic mutation responsible for the patient’s bone marrow failure phenotype has not been identified including the following:

1. Shwachman-Diamond syndrome

- Pancreatic isoamylase, trypsinogen, or fecal elastase
- Abdominal ultrasound demonstrating fatty pancreas
- Imaging demonstrating skeletal abnormalities

2. Diamond Blackfan anemia

- eADA if available at diagnosis prior to transfusions
- Hemoglobin F
- Reticulocyte count
- Bone marrow demonstrating a deficiency of erythroid precursors in an otherwise cellular bone marrow

3. Congenital sideroblastic anemia

- Bone marrow demonstrating the presence of ringed sideroblasts
- Lead and zinc level testing to exclude an acquired cause of ringed sideroblasts

4. Congenital amegakaryocytic thrombocytopenia

- Bone marrow demonstrating megakaryocyte hypoplasia
- 2. History, physical exam, height, and weight.
- 3. Additional labs (if performed):
 - a. CBC with differential
 - b. Liver function studies: ALT, AST, alkaline phosphatase, and total bilirubin/direct bilirubin
 - c. BUN/creatinine
 - d. Serum ferritin and % iron saturation
 - e. Additional labs deemed clinical important for review by the treating physician for review by the ERC
- 4. Bone Marrow Evaluation (if performed):
 - a. Bone marrow aspirate/biopsy for pathology, flow cytometry, cytogenetics and MDS FISH panel. The MDS FISH panel should evaluate for deletion 5q/monosomy 5, monosomy 7/deletion 7q, trisomy 8, and deletion 20q. Given the complexities of diagnosing MDS in patients with BMFD, the ERC will review all pre-transplant bone marrow evaluations in patients who lack a genetic mutation as well as review all patients with bone marrow evaluations concerning for possible MDS in order to aid with the diagnosis of MDS. This is particularly important as we do not want to exclude potentially eligible patients due to an incorrect diagnosis of MDS.
- 5. Procedures/Imaging (if performed):
 - a. Assessment of hepatic and potentially cardiac (age ≥ 18 years old) iron status is required for all patients with a history of significant transfusions defined as ≥ 8 packed red blood cell transfusions per year for ≥ 1 year or have received ≥ 20 packed red blood cell transfusions (lifetime cumulative). In addition, patients with prior history of elevated hepatic or cardiac iron will require formal assessment prior to study enrollment. Formal assessment will include a liver MRI using a validated methodology such as T2* MRI or ferriscan or liver biopsy as well as formal assessment of cardiac iron content using T2* MRI.
 - b. Additional imaging deemed clinical important by the treating physician for review by the ERC.

All uploaded source documentation must be de-identified, including redaction of all patient identifiers and/or PHI (name, patient initials, medical record number, date of birth) as well as redaction of institutional name and physician/advanced practice provider name(s).

Following completion of Segment 0 enrollment form and upload of source documentation, the DCC protocol coordinator will be notified via email. The protocol coordinator will review the data and source documentation in Advantage eClinical. If all case information is present, the protocol coordinator will alert the protocol ERC. The ERC will review the case at the next scheduled ERC meeting which usually occurs weekly. The protocol coordinator will notify the enrolling center in writing once the panel has completed their review.

